6.3.2 Participant Demographics and Baseline Characteristics

Participant demographics, baseline characteristics, cancer disease history, medical history, prior cancer therapy, and other collected baseline data will be summarized using descriptive statistics.

6.4 Study Drug Exposures and Concomitant Medications

Study drug exposure, dose delay (including number and duration of delay), dose reduction, study drug withdrawals and concomitant medications will be summarized by descriptive statistics.

The summary of study drug exposure will include descriptive statistics as well as frequency counts for the number of doses or cycles received, the total dose administered as well as the total dose intended, and the dose intensity, which is calculated as percentage of total dose actually administrated divided by total dose intended during whole treatment period.

Duration of study treatment in months will be calculated as:

- (end of treatment visit (EOTV) date – first dose date + 1)/(365.25/12) for participants who have discontinued treatment;
- (data cutoff date – first dose date + 1)/(365.25/12) for participants whose treatment is ongoing.

The summary of concomitant medications will include the number and percentage of participants who receive any concomitant medications as well as each concomitant medication by drug class.

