## 9.16 End of Treatment Visit

A list of evaluations to be performed for the EOTV is provided in [Appendix 1](#). The EOTV should be performed after the participant has met study treatment discontinuation criteria specified in [Section 5.4](#); the visit should be performed within 30 days following the last dose of study drug. It is recognized that certain participants (such as those experiencing progression of disease) may be cared for in facilities other than the participating study site, may proceed to receive other cancer therapy, and/or may elect not to return to the study site. Therefore, this visit is considered optional, but should be carried out whenever possible. All required procedures and tests should be performed if the visit is performed. Note: the tumor assessment will not be performed at the EOTV for participants who had a previous scan performed < 28 days of the EOTV.

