**Module A Cohort Expansion Phase**

| EVALUATION/
PROCEDURE | Screening 
(Within
28 days) | Cycle 1 |       |                |                 |                 |                 | Cycle 2 and Subsequent Cycles |                 |                                            | EOTV  | Post
TRT
FUP |
|--------------------------|-------------------------------------------------|---------|-------|----------------|-----------------|-----------------|-----------------|-------------------------------|-----------------|--------------------------------------------|---------------------|--------------------|
|                          |                                                 | Day 1   | Day 2 | Day 8
(±1d) | Day 15
(±1d) | Day 22
(±1d) | Day 42
(±5d) | Day 1
(±1d)                | Day 22
(±1d) | Days 23,
29, 36
(±1d)  |                     |                    |
| Study Day                |                                                 | 1       | 2     | 8              | 15              | 22              | 42              | 43                            | 64              | 65, 71, 78                                 |                     |                    |
| Survival Follow-up       |                                                 |         |       |                |                 |                 |                 |                               |                 |                                            |                     | X                  |

Survival follow-up collected every 3 months (90 days ± 7 days) by clinic visit, telephone, paper mail, or other electronic contact for 2 years; information regarding response status and/or the occurrence of disease progression may be collected approximately every 3 months in participants who discontinued from study treatment due to reasons other than progressive disease, if they have not initiated any other cancer directed therapy. See [Section 9.17](#) for details.

1 The Screening visit should occur within 28 days prior to Day 1.

2 All laboratory tests and body weight may be performed up to 24 hours prior to each treatment visit.

3 For ≥ Cycle 2 Visits on Days 23, 29, and 36 are remote telemedicine visits only.

4 The EOTV should be performed within 30 days following the last dose of study drug.

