6.2 Missing Data

Data that are reported as missing will be treated as missing in all data summaries. Imputation rules for partially recorded dates, in case that the complete dates are required to carry out an analysis, will be provided in the Statistical Programming Plan (SPP). In descriptive summaries for safety, observations that are spurious (extreme relative to the majority of the data) will not be altered or removed from the summary.

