6.7.5 Analyses of Metastatic Castration-resistant Prostate Carcinoma-specific Endpoints

- rPFS: The censoring rules in [Table 2](#) will be applied to rPFS analysis. The analysis of rPFS will be the same as that described for PFS.
- PSA:

PSA response rate will be calculated for participants with a baseline PSA ≥ 2 ng/mL and at least 1 post-baseline value (i.e. PSA response evaluable population). The PSA response rate will be summarized at 12 weeks from baseline. The 2-sided 95% exact binomial CI of the response rate will be calculated.

The percent change in PSA from baseline overall time will be summarized by visit and presented individually by spider plot. The percentage of change in PSA from baseline to 12 weeks (or earlier if treatment is discontinued), and the best PSA percent change from baseline will be presented by waterfall plots.

The Kaplan-Meier method will be applied to estimate time to PSA progression in the PSA response evaluable population. PSA measurements are performed at baseline and then repeated prior to each dose of each treatment visit, approximately 30 days after the last study treatment administration (EOTV), and every 12 weeks (± 7 days) during the follow-up period until disease progression, start of another cancer therapy, or the study cutoff date, whichever comes first.

Participants without PSA progression at the time of analysis will be censored to the date of their last PSA assessment. The last three rules in **Table 2** will be applied to PSA progression analysis, with the changes from “progression” and “tumor assessment” to “PSA progression” and “PSA assessment”, respectively.

- SSE: SSE rate will be summarized. Specifically, SSE rate per 100 patient-year will be calculated as the number of each of the SSEs, including the occurrence of new symptomatic pathological fracture, use of external beam radiation to relieve bone pain, spinal cord compression, or tumor-related orthopedic surgical intervention, divided by the total patient-years in the mCRPC cohort. The Kaplan-Meier method will be applied to estimate time to SSE. Participants without SSE at the time of analysis will be censored at the last assessment. For each participant, the eCRF documenting any SSEs is scheduled to be completed pre-dose of each treatment. Participants without any SSE assessment will be excluded for the SSE endpoint analysis.

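### SAP 6.4 ends treatment duration at an optional visit up to 30 days after the last dose, so the figure shifts with visit timing and cannot be computed without that visit

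*SAP*

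**What the plan says.** SAP Section 6.4 gives two formulas for duration of study treatment in months. For participants off treatment it is "end of treatment visit (EOTV) date – first dose date + 1)/(365.25/12) for participants who have discontinued treatment". For the rest it is "data cutoff date – first dose date + 1)/(365.25/12) for participants whose treatment is ongoing".

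Protocol Section 9.16 describes the visit that supplies the first end date. It takes place once a discontinuation criterion has been met, and "the visit should be performed within 30 days following the last dose of study drug". The Module A Cohort Expansion schedule in Appendix 1 repeats the window: "The EOTV should be performed within 30 days following the last dose of study drug". Section 9.16 also recognises that some participants, such as those who progress, "may proceed to receive other cancer therapy, and/or may elect not to return to the study site". It concludes: "Therefore, this visit is considered optional, but should be carried out whenever possible".

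In its PSA text, SAP Section 6.7.5 describes the same visit as "approximately 30 days after the last study treatment administration (EOTV" and so puts it near the late end of the window.

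SAP Section 6.4 names no substitute date when the visit did not happen. The general rule in SAP Section 6.2 is: "Data that are reported as missing will be treated as missing in all data summaries". That section sends only partially recorded dates to the Statistical Programming Plan (SPP) for imputation.

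**The concern.** The EOTV is a post-treatment assessment. Its date depends on when the participant could attend, not on when drug was last given. Using it as the end of treatment has two effects. Days off drug are counted as days on treatment, and two participants with the same dosing history can get different durations. A participant who stopped and never had the visit has no end date.

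What is at stake is one line of the exposure summary: the mean, median and range of treatment duration by dose level and cohort. Readers use that line to judge how long a regimen was tolerated, and many durations in a population with advanced disease could be short enough for a few weeks to show.

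**Working it through.** **Inputs**
- Month length: 365.25/12 = 30.4375 days (SAP 6.4).
- Gap g from last dose to EOTV: 0 to 30 days (Protocol 9.16, Appendix 1).
- Dosing on Days 1 and 22 of each 42-day cycle, so every 21 days (Protocol 6.1); at most 18 cycles, or 36 doses (Protocol 4.1).
- Assumption, not in the documents: if the final dosing interval counts as treatment, it ends 20 days after the last dose.

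The plan states no duration figure, so there is none to reproduce.

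**Formulas.** With no delays, dose n falls on study day L = 1 + 21(n - 1).
- SAP rule: (L + g)/30.4375
- To last dose: L/30.4375
- To end of final interval: (L + 20)/30.4375

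**Difference per participant.** This does not depend on the number of doses.
- SAP rule minus last dose = g/30.4375. For g = 0, 14, 21 and 30 days this is 0, 0.46, 0.69 and 0.99 month.
- SAP rule minus end of interval = (g - 20)/30.4375. For g = 0, 14 and 30 days this is -0.66, -0.20 and +0.33 month.

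**Relative size at the latest visit inside the window (g = 30), in months**

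| Doses | SAP rule | To last dose | Excess | To last dose + 20 days | Excess |
|---|---|---|---|---|---|
| 2 | 52/30.4375 = 1.71 | 22/30.4375 = 0.72 | +136% | 42/30.4375 = 1.38 | +24% |
| 4 | 94/30.4375 = 3.09 | 64/30.4375 = 2.10 | +47% | 84/30.4375 = 2.76 | +12% |
| 8 | 178/30.4375 = 5.85 | 148/30.4375 = 4.86 | +20% | 168/30.4375 = 5.52 | +6% |
| 36 | 766/30.4375 = 25.17 | 736/30.4375 = 24.18 | +4% | 756/30.4375 = 24.84 | +1% |

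**The window is not a hard cap.** The 30 days are worded as what should happen. Protocol 5.4 also lists a dose delay of more than 21 days due to AEs as a reason to stop. If that delay is counted from the planned infusion date, as Protocol 4.4.1 does, the criterion is met more than 21 + 21 = 42 days after the last dose. A visit held after that point gives a gap above 42/30.4375 = 1.38 months.

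**No visit.** Death is a listed reason for stopping treatment (Protocol 5.4), and Section 9.16 expects some participants not to return. Without an EOTV date the formula for discontinued participants cannot be evaluated. SAP 6.2 does not fill the hole, because an absent visit is not a partially recorded date.

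**The case against.** The strongest reply is that little depends on this line. SAP 6.4 summarises exposure mainly through doses or cycles received, total dose administered and intended, and dose intensity, which is a ratio of doses. None of these uses the EOTV date. Adverse events are tabulated as numbers and percentages of participants, with no exposure-adjusted rate. The only rate per patient-year is for skeletal events (SAP 6.7.5), and it is not tied to this formula. This stands. A reader might infer that exposure as a whole is overstated, or that the primary safety objective is affected; the documents support neither.

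Second, nothing in the documents says that treatment ends on the day of the last infusion. For a drug given every three weeks it is defensible to count the final interval, and then an early EOTV understates duration. This also stands. A more than twofold inflation after two doses is tempting to quote, but it holds only against the last infusion day and with the visit at day 30.

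Third, a reader might infer that missing durations fall mainly on participants with short treatment and so push the average up. Section 9.16 mentions progression as an example and does not say when it occurs; progression can come early or late. The direction of any such bias is not established.

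Fourth, the SPP, which is not among the documents, may contain a fallback date. That cannot be excluded. It would not change the end date the SAP sets for participants who do have the visit.

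**Conclusion.** The point holds for the treatment-duration summary only. As written, the SAP takes the end of treatment from an optional visit with a flexible date. Within the 30-day window the result exceeds duration to last dose by 0 to 0.99 month per participant. If the final dosing interval is counted, an assumption, the result differs by -0.66 to +0.33 month. The true average gap is unknown, although the SAP's own description puts the visit near day 30. For discontinued participants without an EOTV, the SAP gives no computable value.

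Either benchmark is a reasonable definition of treatment duration; the visit date matches neither. Because the measure is descriptive and feeds no endpoint or dose decision, this is a correction to make before the analysis, not a threat to the study's conclusions.

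**What to change.** In SAP Section 6.4, replace the EOTV date in the formula for discontinued participants with the date of the last dose of study drug: (last dose date - first dose date + 1)/(365.25/12). If the final dosing interval is meant to count, use last dose date + 20 days, capped at death or data cutoff. State which convention applies.

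Apply the same convention to ongoing participants, who now run to data cutoff; otherwise the two groups are measured differently. Under the second option one rule serves both: an ongoing participant on schedule is within 20 days of the last dose at cutoff, so the cap returns the cutoff date, as the current formula does.

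The cost is small. Infusion start and end dates are already recorded on the eCRFs (Protocol Appendix 3), and every dosed participant has a last dose, so duration becomes computable for all of them. Reported durations may become slightly shorter.

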6.5 Subsequent Anti-cancer Therapy

Systemic anti-cancer therapies received after study drug discontinuation may include chemotherapy, immunotherapy, biologic therapy, targeted small molecules, radiotherapy, and surgery. Number and percentage of participants with any subsequent anti-cancer therapy will be summarized.

6.6 Protocol Deviations

Major protocol deviations will be identified prior to database lock for final analysis and will be listed and summarized.

6.7 Efficacy Endpoint Analyses

6.7.1 Analyses of Response Endpoints

The number and percent of participants with their BOR will be summarized. The objective response rate (ORR) per RECIST v1.1 is estimated as the proportion of participants in the response evaluable population who achieve BOR of CR or PR. The 2-sided 95% exact binomial CIs of the response rates will be calculated.

6.7.2 Analyses of Time-to-event Endpoints

6.7.2.1 Analyses of Progression-free Survival

The Kaplan-Meier method will be applied to estimate PFS curve, median PFS, and PFS rates at 3 and 6 months. The method of Brookmeyer and Crowley (1) will be used to construct 95% CI for median PFS. The 95% CIs for PFS rate will be calculated by normal approximation after log(-log) transformation.

For patients who are not known to be dead or progressed at the time of data cut-off for PFS analysis, the PFS will be censored at the date of the last tumor assessment. For primary PFS analysis, Table 2 describes the censoring rules.

Table 2 Censoring Rules for Primary Progression-free Survival Analysis

Situation	Date	Outcome
No baseline tumor assessments	First dose date	Censored
Death prior to first scheduled tumor assessment	Date of death	Progressed
No post-baseline tumor assessments in absence of death prior to first scheduled tumor assessment	First dose date	Censored
Documented progression	Date of progression	Progressed
Initiation of alternative anti-cancer treatments in absence of documented progression	Date of last tumor assessment prior to initiation of such treatment	Censored
Death or documented progression immediately after missing two or more consecutive scheduled tumor assessments	Date of last tumor assessment prior to missed assessments	Censored

PFS will be analyzed by tumor type when sample size warrants. A sensitivity analysis for PFS may be performed to assess the robustness of above primary PFS analysis. For this sensitivity analysis, the censoring rules are the same as in **Table 2** except that the documented progression or death will be considered as an event, regardless when it occurs during the study.

6.7.2.2 Analyses of Duration of Response

The Kaplan-Meier method will be applied to estimate DoR curve and median DoR. The last three censoring rules described in **Table 2** will be applied for handling censorings. For responders (see definition in [Section 5.1.2](#)) who are not known to be dead or progressed at the time of data cut-off for DoR analysis, the DoR will be censored at the date of the last tumor assessment. The method of Brookmeyer and Crowley ([1](#)) will be used to construct 95% CI for median DoR. The DoR analyses will be performed only if there are enough responders to render the analyses meaningful.

6.7.2.3 Analyses of Overall Survival

The Kaplan-Meier method will be applied to estimate OS curve, median OS, and OS rates at 6 and 12 months. For patients who are not known to be dead at the time of data cut-off for OS analysis, the OS will be censored at the time they are last known to be alive. The method of Brookmeyer and Crowley ([1](#)) will be used to construct 95% CI for median OS. The 95% CIs for OS rate at 6 and 12 months will be calculated by normal approximation after log(-log) transformation. OS will be analyzed by tumor type when sample size warrants.

6.7.3 Subgroup and B7-H3 Expression Analyses

Subgroup analysis of efficacy (e.g., objective response rate, PFS and OS) may be conducted based on the following biomarkers:

Microsatellite instability-high (MSI-H) status

BRCA-1 mutation

BRCA-2 mutation

BRAF mutation (melanoma only)

Human papilloma viral status (SCCHN only)

The relationship between B7-H3 expression IHC score and clinical response will be explored.

6.7.4 Tumor Size Change Over Time

The tumor size percent change from baseline over time will be summarized and presented by spider plot. The best tumor size percentage change from baseline will be presented by waterfall plot.

6.7.5 Analyses of Metastatic Castration-resistant Prostate Carcinoma-specific Endpoints

- rPFS: The censoring rules in [Table 2](#) will be applied to rPFS analysis. The analysis of rPFS will be the same as that described for PFS.
- PSA:

PSA response rate will be calculated for participants with a baseline PSA ≥ 2 ng/mL and at least 1 post-baseline value (i.e. PSA response evaluable population). The PSA response rate will be summarized at 12 weeks from baseline. The 2-sided 95% exact binomial CI of the response rate will be calculated.

The percent change in PSA from baseline overall time will be summarized by visit and presented individually by spider plot. The percentage of change in PSA from baseline to 12 weeks (or earlier if treatment is discontinued), and the best PSA percent change from baseline will be presented by waterfall plots.

The Kaplan-Meier method will be applied to estimate time to PSA progression in the PSA response evaluable population. PSA measurements are performed at baseline and then repeated prior to each dose of each treatment visit, approximately 30 days after the last study treatment administration (EOTV), and every 12 weeks (± 7 days) during the follow-up period until disease progression, start of another cancer therapy, or the study cutoff date, whichever comes first.

Participants without PSA progression at the time of analysis will be censored to the date of their last PSA assessment. The last three rules in **Table 2** will be applied to PSA progression analysis, with the changes from “progression” and “tumor assessment” to “PSA progression” and “PSA assessment”, respectively.

- SSE: SSE rate will be summarized. Specifically, SSE rate per 100 patient-year will be calculated as the number of each of the SSEs, including the occurrence of new symptomatic pathological fracture, use of external beam radiation to relieve bone pain, spinal cord compression, or tumor-related orthopedic surgical intervention, divided by the total patient-years in the mCRPC cohort. The Kaplan-Meier method will be applied to estimate time to SSE. Participants without SSE at the time of analysis will be censored at the last assessment. For each participant, the eCRF documenting any SSEs is scheduled to be completed pre-dose of each treatment. Participants without any SSE assessment will be excluded for the SSE endpoint analysis.

6.7.6 Patient-reported Outcome

The BPI-sf will be used to assess pain. A mean pain severity score will be calculated from the average of 4 pain intensity item scores: items 3 (worst), 4 (least), 5 (average), and 6 (right now). Changes from baseline in pain intensity item scores, mean pain severity score, and pain interference scores will be summarized. Imputation of missing values will be used for BPI-sf. If at least two out of the four pain intensity items are answered, any missing items will be assigned the mean value of the completed pain intensity items. If at least four out of the seven pain interference items are answered, the missing pain interference items will be assigned the mean value of the completed pain interference items.

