## **9.15      Patient-reported Outcome**

Patient reported outcome (PRO) will be assessed using the BPI-sf ([Appendix 6](#)). The BPI-sf is an exploratory 9 item self-administered written questionnaire used to evaluate the severity of a participant's pain and the impact of the pain on daily functioning. The participant will be asked to rate their "worst," "least," "average," and "right now" (current) pain intensity on a

10-point scale ranging from zero (no pain) to 10 (pain as bad as you can imagine). Participants will also be asked to list their current treatments for pain and their perceived effectiveness (on a scale of 0% to 100%), and to rate the degree that pain interferes with 7 daily activities (general activity, mood, walking ability, normal work, relations with other persons, sleep, and enjoyment of life) on a 10 point scale ranging from zero (does not interfere) to 10 (completely interferes).

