2.3 Exploratory Objectives

- To explore patient-reported outcome (PRO) using the Brief Pain Inventory-short form (BPI-sf) in Cohort Expansion (Module A).
- To explore effect of MGC018 on symptomatic skeletal events (SSEs) in participants with mCRPC in Cohort Expansion (Module A).
- To explore the relationships between PK, pharmacodynamics of MGC018 alone and in combination with MGA012, and antitumor activity (Modules A and B).
- To explore the impact of MGC018 alone and in combination with MGA012 on progression-free survival (PFS) and overall survival (OS) in participants with advanced solid tumors (Modules A and B).
- To determine programmed death-ligand 1 (PD-L1) expression via immunohistochemistry (IHC) staining of formalin-fixed, paraffin-embedded tumor biopsy specimens on archival tissue (Module B) and on optional paired tumor biopsy specimens (pre/on-treatment post Cycle 1 biopsies) in Cohort Expansion (Modules A and B).
- To explore the relationship between B7-H3 expression (H-score) and clinical response using a qualified B7-H3 IHC assay (Modules A and B).

- To assess whether MGC018 in combination with MGA012 induces immunological cell death (ICD) within optional paired tumor biopsy specimens (pre/on-treatment post cycle 1 biopsies) from participants in Cohort Expansion (Module B) as assessed by IHC.
- To assess whether MGC018 in combination with MGA012 modulates immune cell subset phenotype (including PD-1 expression) (Module B).
- To explore whether MGC018 modulates T cell response within optional paired tumor biopsy specimens (pre/on-treatment post Cycle 1 biopsies) from participants in Cohort Expansion (Modules A and B) as assessed by IHC and/or T cell receptor (TCR) spectratyping.
- To assess whether MGC018 alone or in combination with MGA012 induces an interferon gamma (IFN γ) gene expression signature in the optional paired tumor biopsy specimens (pre/on-treatment post Cycle 1 biopsies) from participants in Cohort Expansion (Modules A and B) via transcript profiling.
- To explore serum biomarkers including, but not limited to, IFN γ protein signature, in the peripheral circulation within the Cohort Expansion only (Modules A and B).
- To assess whether MGC018 modulates serum cytokine levels in Dose Escalation and Cohort Expansion phases (Modules A and B).
- To determine MGA012 receptor occupancy on immune cells in participants treated with the combination of MGC018 and MGA012 (Module B only).

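### Mean-filling of missing BPI-sf pain items reaches the item-level summaries, where a filled 'worst' can never be too high and a filled 'least' never too low

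*SAP*

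**What the plan says.** SAP 6.7.6 builds a mean pain severity score from four intensity items: "items 3 (worst), 4 (least), 5 (average), and 6 (right now"). It then states: "Changes from baseline in pain intensity item scores, mean pain severity score, and pain interference scores will be summarized". So each intensity item gets its own change-from-baseline summary, alongside the composite.

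The missing-data rule follows in the same paragraph. "If at least two out of the four pain intensity items are answered", then "any missing items will be assigned the mean value of the completed pain intensity items". The wording is about items. It is not confined to the composite score, and neither worst nor least is exempt. A parallel rule fills missing interference items when four or more of the seven are answered.

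Protocol 14.6.5 names the same summaries and gives no imputation rule. The general rule in SAP 6.2 is different: "Data that are reported as missing will be treated as missing in all data summaries". Protocol 9.15 scores each item from 0 to 10. SAP 2.3 lists the BPI-sf as exploratory, in the Module A Cohort Expansion.

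**The concern.** The four intensity items are not interchangeable measures of one quantity. By their names, worst and least are the ends of a range and the other two lie inside it. Replacing an end of the range with the mean of the remaining answers pulls it inward. That is a reasonable way to obtain a composite from an incomplete form, but it is a poor estimate of the end itself.

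At stake are the item-level rows, in particular change in worst pain. Each filled value there carries an error whose direction is fixed by the rule, and it can contradict what the participant wrote on the same form. With up to 16 participants per expansion cohort, a few such values could be visible in a cohort mean.

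**Working it through.** The documents give no sample size, power or expected missingness for the BPI-sf, so there is no planned figure to reproduce. The check is of the rule itself.

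**Inputs.** W, L, A and N are worst, least, average and right now, each an integer from 0 to 10 (SAP 6.7.6; Protocol 9.15). One or two items may be missing (SAP 6.7.6). Assumption, taken from the item names: L ≤ A ≤ W and L ≤ N ≤ W.

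**Direction.** The filled value is the mean of the answered items. If W is missing, every answered item is at most W, so their mean is at most W. If L is missing, every answered item is at least L, so their mean is at least L. Equality needs all the answered items to equal the missing one.

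**Enumeration.** There are 1,716 ordered answer sets. The error is the filled value minus the true value.

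| Missing | Item filled | Range of error | Too low | Equal | Too high |
|---|---|---|---|---|---|
| W only | W | −10 to 0 | 99.4% | 0.6% | 0% |
| L only | L | 0 to +10 | 0% | 0.6% | 99.4% |
| W and L | W | −10 to 0 | 96.2% | 3.8% | 0% |
| A only (same for N only) | A (or N) | −6.67 to +6.67 | 47.1% | 5.7% | 47.1% |

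The sign for W and L holds in every two-item pattern. These percentages weight all answer sets equally and are not expected trial frequencies; only the sign carries over.

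**A value that conflicts with the same form.** L = 2, A = 4, N = 3, W missing: filled W = (2 + 4 + 3)/3 = 3.0, although W cannot be below the reported average of 4. If the true worst were 7 (an assumed value), the error would be 3 − 7 = −4.

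**Effect on change from baseline.** Take W = 8, L = 2, A = 5, N = 4 at both visits, so the true change is 0.

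- Filled W = (2 + 5 + 4)/3 = 3.67. Missing after baseline: change = 3.67 − 8 = −4.33, a false improvement. Missing at baseline: change = 8 − 3.67 = +4.33, a false worsening.
- Filled L = (8 + 5 + 4)/3 = 5.67. Missing after baseline: change = 5.67 − 2 = +3.67. Missing at baseline: −3.67.
- Both W and L missing: each is filled with (5 + 4)/2 = 4.5, so worst and least become identical.

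**Effect on the composite.** With W missing, the filled severity score is (2 + 5 + 4 + 3.67)/4 = 3.67, the same as the mean of the three answered items. Filling at item level therefore gives the same score as averaging the completed items. Against the true score, (8 + 2 + 5 + 4)/4 = 4.75, both give 3.67 with W missing and 5.67 with L missing.

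**Scale in a cohort (illustration).** One −4 error among 16 participants moves the mean change by 4/16 = 0.25 points.

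**The case against.** The strongest reply is that the rule may be meant only as a scoring rule. Completeness thresholds of 2 of 4 and 4 of 7 are typical of proration for composites, and SAP 7 leaves programming specifications to a separate statistical programming plan, which could restrict the filled values to the scores. This stands in part: the SAP does not expressly say that the item-level rows use filled values. But it assigns values to items, in the paragraph that summarises those items, without a restriction. That is the plain reading, and the text should not depend on another document to reverse it.

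The ordering is also an assumption. The form in Protocol Appendix 6 is not reproduced in the text reviewed, so recall periods could not be checked. It is self-administered, and no consistency check is stated. An inconsistent set (worst 5, least 3, average 5, right now 8) would give a filled worst of (3 + 5 + 8)/3 = 5.33, above 5. This limits the claim to logically ordered answers.

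A rule of some kind is needed, since a score defined as the average of four items does not otherwise exist for an incomplete form. That stands, and the fix keeps the rule for that purpose.

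A reader might infer that SAP 6.7.6 contradicts SAP 6.2. The documents do not support this: the explicit BPI-sf rule is specific and overrides the general one. SAP 6.2 merely lacks the exception clause that SAP 6.1 has for its own list.

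**Conclusion.** The point holds as a minor one. On the plain reading of SAP 6.7.6, filled values enter the item-level change summaries. For logically ordered answers, a filled worst cannot overstate and a filled least cannot understate.

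Two stronger readings are tempting and should be resisted. One is that a filled worst must be too low: equality is possible, so the correct statement is that it cannot be too high. The other is that reported change in worst pain is biased toward improvement overall. That is so only for items missing after baseline; missing at baseline reverses the sign, and the net direction depends on a missingness pattern that the documents do not describe.

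For the same reason no group-level size can be given; the 0.25-point figure is one assumed case. The BPI-sf is exploratory, summarised descriptively with no test or decision attached, and under SAP 2.3 exploratory results may be left out of the clinical study report. No primary or secondary conclusion is affected.

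**What to change.** In SAP 6.7.6, state that the mean of the completed items is used only to form the mean severity score (two or more of four items answered) and the interference score (four or more of seven), and that individual items stay missing in item-level summaries.

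The severity score does not change. Imputation error in the item rows becomes zero by construction, although observed-only item summaries are not thereby shown to be free of bias from who left items blank. The severity score also keeps its own proration bias when worst or least is missing, and a short note should say so.

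The cost is one SAP sentence and slightly fewer observations in the item-level rows. As an optional tidy-up, SAP 6.2 could add an exception for rules specified elsewhere.
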